**Effect of Vitamin D3 on Lung Function and Exercise
Tolerance in D3 Deficient COPD Patients**

ClinicalTrials.gov ID: NCT03781895

Document Date: December 23, 2018

PROJECT SUMMARY

Background: Chronic Obstructive Pulmonary Disease (COPD) is a major cause of morbidity and mortality throughout the world which is a preventable as well as treatable disease. It has some important extra pulmonary effects which may contribute to the magnitude of the severity of this disease. Standard therapeutic treatment alone does not optimize its remedy. Vitamin D₃ has been found to improve the physical efficiency of patients with various morbid disorders, including respiratory ailments. **Objectives:** To evaluate the effects of Vitamin D₃ on lung functions and exercise tolerance in patients with stable moderate COPD. **Methods:** For this, a prospective interventional randomized double blinded study will be carried out on 46 (eighty) vitamin D₃ deficient (serum 25 dihydroxycholecalciferol less than 30 ng/ml), male, stable (diagnosed patient, who has not experienced any acute exacerbation, hospitalizations, urgent care visits, or changes in routine medication within 4 weeks prior to study), moderate (post bronchodilator FEV₁/FVC < 0.70 of predicted value and FEV₁ = 50 to 79% of predicted value) COPD patients (age ≥ 40 years), who will be selected from the Out Patient Department (OPD) of the National Institute of Diseases of Chest and Hospital (NIDCH) and will be grouped as A (control) and B (study) groups, respectively. All the patients will be again designated as A0, A90 (with placebo) and B0, B90 (with D₃) for before and after 90 days of follow up. All the participants will be matched in terms of duration of COPD, history of smoking, occupation and socioeconomic status. Along with the standard pharmacological treatment of COPD, the patients of the 'Study group' will be prescribed for 80000 IU of oral vitamin D₃ per week for consecutive 3 months. Along with this, all patients both the groups will be advised to continue ad lib (according to their own choice) diet. At the very 1st day of the study, the lung functions will be assessed by measuring Forced vital capacity (FVC), Forced expiratory volume in one second (FEV₁), Forced expiratory ratio (FEV₁/FVC%), Peak expiratory flow rate (PEFR) and Forced mid expiratory flow of FVC (FEF_{25-75%}), with a portable digital spirometer. In addition, exercise tolerance will be assessed by change in 6 Minute Walk Distance (6MWD) in 6 Minute Walk Test (6MWT). Changes in peripheral capillary oxygen saturation (SpO₂) by Pulse Oximeter and degree of dyspnoea by Modified Borg Scale (MBS) will also be measured both before and after 6MWT to evaluate their change in both the groups. All these variables will be measured again after 90 days standard pharmacological treatment of COPD with D₃ intervention (B group) and also without D₃ intervention (A group). For statistical analysis, Chi-square test, independent sample 't' test between two groups, paired

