Alternate: Vitamin D₃ administration improves lung function and exercise tolerance in vitamin D₃ deficient stable COPD patients.

Objectives:

General Objective

To evaluate the effects of vitamin D₃ administration on lung functions and exercise tolerance in vitamin D₃ deficient male patients with stable COPD.

Specific Objectives

[figure not shown]
- To measure the FVC, FEV₁, FEV₁/FVC%, PEF and FEF_{25-75%} of vitamin D₃ insufficient male patients with stable moderate COPD, in order to assess their lung function status.
- To measure the SpO₂ at rest, in order to assess the basal oxygenation status in this group of patients.
- To determine level of dyspnea at rest, in order to assess the basal breathlessness level in the same group of patients
- To measure the 6MWD of all the patients, in order to assess their functional exercise capacity.
- To measure both the SpO₂ and level of dyspnea again after 6MWT, for the assessment of their exercise tolerance.
- To measure all these variables after 90 days standard pharmacological treatment with vitamin D₃ and also without vitamin D₃ in stable COPD patients.
- To compare the results of baseline and endline.

Methodology:

Consolidated Standard of Reporting Trials:

(Moher et al 2010)

CONSORT 2010 Flow Diagram

TYPE OF STUDY : Prospective interventional randomized double blinded study

PLACE OF STUDY : Department of Physiology, Bangabandhu Sheikh Mujib Medical University (BSMMU), Shahbagh, Dhaka

STUDY PERIOD : March 2017 to February 2018

STUDY POPULATION : Stable, moderate COPD patients with vitamin D₃ deficiency.

SAMPLE SIZE : 46

SAMPLING : Simple random sampling .

GROUPING OF THE SUBJECTS :

Group A : 23 D₃ deficient COPD patients without D₃ administration
(Control group)

A0 : On day 0

A90 : On day 90

Group B : 23 D₃ deficient COPD patients with D₃ administration
(Study group)

B0 : On day 0

B90 : On day 90

Subject Selection:

Inclusion Criteria

- Age: >40 years (Heideri 2015)
- Socioeconomic condition: Middle class (Martineau et al 2015)
- Smoking status: (Janssens et al 2010)
 - Current smoker = with history of active smoking
 - Ex-smoker = with history of 0 – 8 quit year
 - Duration = for >30 pack years
- BMI: 25 – 29.9 kg/meter-sq (Janssens et al 2010)
- COPD patients at moderate stage according to GOLD criteria with > 4 years duration (Rees et al 2013)
- Stable COPD patients (Mehrparver et al 2010)
- Vitamin D₃ deficient: 30 ng/ml (Vitamin D Council 2017)

Exclusion Criteria

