All the above mentioned variables will be similar ,statistically non significant in both the groups to ensure the minimization of their effects.

VITAMIN ADMINISTRATION :

Collection:

Vitamin D3

Ingredient

- Cholecalciferol (40,000IU)
- Microcrystalline Cellulose (58.1 gm)
- Butylated Hydroxy Toluene (0.2mg)
- Magnesium Stearate (3mg)
 - Gelatin Capsule Shell (1mg)

Dose : 80,000 IU/wk

Route : Oral

Placebo : Courtesy of Beximco Pharmaceuticals Limited Bangladesh

Ingredient : • Microcrystalline Cellulose (303.8gm) • Butylated Hydroxy Toluene (0.2mg)

- Magnesium Stearate (3mg)
- Gelatin Capsule Shell (1mg)

STUDY VARIABLES:

(1) Spirometric variables

- FVC (L) : Forced Vital Capacity
- FEV₁ (L) : Forced Expiratory Volume in 1st second
- FEV₁/FVC Ratio (%) : Forced Expiratory Ratio
- PEF_R (L/min) : Peak Expiratory Flow Rate
- FEF₂₅₋₇₅ (L/S) : Forced Expiratory Flow in the middle of FVC

(2) Oxygenation variables

- Resting SpO₂ (%) : Resting Peripheral Capillary Oxygen saturation

(3) Exercise tolerance variables

- 6MWD (meter) : Six Minute Walk Distance
- Level of Dyspnea : Modified Borg Scale

(4) Hematological variables

- 25(OH)D (ng/ml) : 25-hydroxycholecalciferol
- PTH (pmol/l) : Parathyroid hormone
- Ca²⁺ (mg/ml) : Ionic calcium
- PO₄³⁻ (mg/ml) : Ionic phosphate
- AP (U/L) : Alkaline Phosphatase

Subsequently a standard therapeutic treatment (according to GOLD guideline) (Annexure - VI) will be prescribed to all the selected stable moderate COPD patients. In addition, the patients of

the 'Study group' will be prescribed for 80000 IU of oral vitamin D₃ per week for consecutive 90 days . Along with this, all the patients of both the groups will be advised to continue ad lib (according to their own choice) diet.

Proper education will be given about drug , method of taking medication and medication plan. Afterwards, a good rapport will be built up to take time to time follow up over telephone and visiting patient's place . Schedule appointment , hotline and follow up will be maintained properly. They will be requested to attend the Department of Physiology again on the 90th day, to have the assessment of all the above-mentioned study variables

Any patient, who failed to follow the study procedure exactly during study period, will be dropped and a new one will be included to fulfill the desired total sample number. That's why extended sample should be taken to fulfill the total sample number.

Collection of blood sample (Afroza 2015):

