The 6MWT will be performed at indoors, along a long, flat, straight, enclosed corridor with a hard surface that is seldom traveled. The walking course will be 30 meter in length which will be marked every 3 meter. The turnaround points will be marked with a cone. A starting line, which marked

the beginning and end of each 60 meter lap, will be marked on the floor using brightly colored tape.

The subject will be asked to walk at his own maximal pace along the corridor from the end, covering as much ground as he can, during the allotted time, without running. He will be also advised to take rest if he will be too exhausted to continue the test. Standard phrases at regular intervals (every 60 seconds) will be used, like: “you are doing well,” “keep up the good work”. At the same time he will be also informed about the past time and how much has left before the test was completed.

If any of the subjects developed chest pain, intolerable dyspnoea, leg cramps, staggering, diaphoresis or pale appearance the test will be immediately stopped and the subject will be dropped. Again, when any subject will complete the total study procedure (according to the exact study design), he will be congratulated for good effort.

STATISTICAL ANALYSIS:

The results will be expressed as mean with standard deviation (mean \pm SD).

The data will be statistically analyzed by a computer with SPSS (Version 16.0) using Chi-square test,(to know the qualitative difference between the observed and expected result).Spirometric variables, oxygenation variables, exercise tolerance variables and hematological variables will be found between two groups of patients. If the variables are normally distributed , statistical analysis will be done by parametric statistical test. But if it is not normally distributed then it will be transformed into natural logarithm and again into anti logarithm, to make it normally distributed, then parametric statistical test will be done. Independent sample ‘t’ test between two groups, paired Student’s ‘t’ test within two specific measurements of different durations of each group will be done.

In the interpretation of results, ≤ 0.05 level of probability (p) will be accepted as significant.

PUBLICATION POLICY

- ❖ Scientific article to be published in a scientific journal.
- ❖ Presentation in scientific seminar or conference orally or through poster presentation.
- ❖ Website dissemination through internet version of JBSP.

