FEV ₁ /FVC	(%)				
PEFR:	(L/S)				
FEF ₂₅₋₇₅	(L/S)				
MEF ₇₅	(L/S)				
MEF ₅₀	(L/S)				
MEF ₂₅	(L/S)				

(PV=Predicted Value, MV=Measured Value)

Variables	Before	After	Before	After
	(day 0)	(day 0)	(day 90)	(day 90)

Oxygen Saturation % (SpO₂)

Level of dyspnea (Borg Score)

Level of fatigue (Borg Score)

Total Distance (in meter) Walked In 6 Minute :

The Modified Borg Scale:

SCALE	SEVERITY
0	No Breathlessness At All
0.5	Very Very Slight (Just Noticeable)
1	Very Slight
2	Slight Breathlessness
3	Moderate
4	Somewhat severe
5	Severe Breathlessness
6	
7	Very Severe Breathlessness
8	
9	Very Very Severe (Almost Maximum)
10	Maximum

Hematological variables:

Serum 25(OH)D ng/ml

Serum PTH pg/ml

Serum Ca²⁺ mg/dl

Serum IU/L

Alkaline
phosphat
ase

Serum IU/L

SGPT

Serum mg/dl

Creatini
ne

Fasting mg/dl

blood
glucose

Serum %

HbA1c

Serum (mg/dl)

Choleste
rol

Serum (mg/dl)

TG

Serum (mg/dl)

HDL

Serum (mg/dl)

LDL

Serum (mg/dl)

PO₄³⁻

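### The rule for non-normal variables logs and then un-logs the data before the t-test, so it changes nothing, and its log step is undefined for a Borg score of 0

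*Combined protocol and SAP*

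**What the plan says.** The Statistical Analysis section names four groups of variables to be compared between the arms: spirometric, oxygenation, exercise tolerance and hematological. Normally distributed variables go to parametric tests. Any other variable is to be "transformed into natural logarithm and again into anti logarithm, to make it normally distributed, then parametric statistical test will be done". The tests are the independent-sample t-test between groups and the paired t-test "within two specific measurements of different durations of each group will be done". Results are to be expressed as mean with SD. The available text gives no rank test, no added constant, no handling of zeros, and no step for a variable that stays non-normal.

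Dyspnoea falls under this rule. Study Variables, group (3) Exercise tolerance variables, lists "Level of Dyspnea : Modified Borg Scale". The Project Summary says that "degree of dyspnoea by Modified Borg Scale (MBS) will also be measured both before and after 6MWT". The Specific Objectives cover both time points: "To determine level of dyspnea at rest, in order to assess the basal breathlessness level", and "level of dyspnea again after 6MWT, for the assessment of their exercise tolerance". The scale printed in the data sheet starts at 0, labelled "No Breathlessness At All", and runs through 0.5 and 1 up to 10.

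**The concern.** There are two faults.

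1. **Order of the steps.** The antilog comes before the test, and the pair of steps is credited with producing normality. A log followed by an antilog is the identity, so nothing is transformed. An analyst who follows the sentence and one who guesses the intent (test on logs, antilog only for reporting) will get different p-values from the same data.

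2. **Zeros.** Under either reading the first step is ln(x), which does not exist at x = 0. If Borg is judged non-normal and the zeros become missing, the patients removed are those with no breathlessness. If vitamin D3 relieves dyspnoea, more of them are in the study arm. The rule would then drop the best outcomes mainly from one arm, shrink the estimated benefit and reduce power.

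**Working it through.** The plan gives no figure to reproduce here. Its own inputs are 46 patients (23 per group), significance at p ≤ 0.05, and the Borg levels in the data sheet. All distributions, effects and zero shares below are assumptions.

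**Step 1: the identity.** For x > 0, exp(ln x) = x. Check on one simulated lognormal data set, 23 per arm:

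| Data tested | Independent t, p | Paired p | Shapiro-Wilk p, one arm |
|---|---|---|---|
| Raw | −1.298, 0.201 | 0.198 | 0.137 |
| Log then antilog | −1.298, 0.201 | 0.198 | 0.137 |
| Log scale | −0.365, 0.717 | 0.716 | 0.991 |

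The first two rows agree; the stored values differ by at most 8.9 × 10⁻¹⁶, which is rounding. These p-values are illustrations, not trial results.

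**Step 2: cost for strictly positive variables.** Lognormal data, 23 per arm, true shift 0.8 log-SD, two-sided 5%, 100,000 simulated trials per setting. Log-scale power is 76% throughout (exact noncentral t).

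| Log-SD | Power, raw t-test | Type I error, raw |
|---|---|---|
| 0.2 | 75% | 5.0% |
| 0.3 | 74% | 4.9% |
| 0.5 | 71% | 4.9% |

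**Step 3: are Borg zeros likely?** ln(0) gives a domain error; every other level has a finite log, from −0.69 at 0.5 to 2.30 at 10. The chance of at least one zero among 46 is 1 − (1 − p)^46. For p = 2%, 5% and 10% this is 61%, 91% and 99%.

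**Step 4: cost between groups if zeros become missing.** A latent normal score with SD 1.2 is rounded to the printed levels, and values below 0.25 score 0. The true reduction is 0.9. For control zero share p0, the control mean is 0.25 − 1.2·z(p0), which is 2.22, 1.79 and 1.26 for p0 = 5%, 10% and 20%. The study-arm zero share is Φ(z(p0) + 0.9/1.2).

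| | p0 = 5% | p0 = 10% | p0 = 20% |
|---|---|---|---|
| Study-arm zeros | 18.5% | 29.8% | 46.3% |
| Patients lost, 23 × (sum of the two shares) | 5.4 | 9.1–9.2 | 15.2–15.3 |
| Power: untransformed t, all patients | 67% | 66% | 63% |
| Power: Mann-Whitney, all patients | 65% | 65% | 64% |
| Power: t on logs, zeros missing | 44% | 36% | 24% |
| Power: log-antilog then t (literal), zeros missing | 47% | 37% | 24% |
| Mean difference, all patients | 0.84 | 0.78 | 0.67 |
| Mean difference, non-zero scorers only | 0.64 | 0.54 | 0.43 |

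These come from 20,000 trials per setting. Type I error of all four tests stays between 4.7% and 5.2%. The mean differences are on the Borg scale, so the last row belongs to the literal reading. It is lower than the row above by 24% (0.20/0.84), 31% (0.24/0.78) and 36% (0.24/0.67).

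**Step 5: sensitivity at p0 = 10%** (all patients, untransformed t, versus zeros missing, log t):
- SD 1.2, reduction 0.5: 27% versus 16%.
- SD 1.0, reduction 0.9: 81% versus 44%.
- SD 1.5, reduction 0.9: 48% versus 26%.

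**Step 6: few zeros.** With SD 1.2 and reduction 0.9:
- Control mean 3: 23 × [Φ((0.25 − 3)/1.2) + Φ((0.25 − 2.1)/1.2)] ≈ 23 × (0.011 + 0.062) ≈ 1.7 zeros among 46. Log-scale power is about 55%.
- Control mean 4: 23 × [Φ((0.25 − 4)/1.2) + Φ((0.25 − 3.1)/1.2)] ≈ 23 × (0.001 + 0.009) ≈ 0.2 zeros. Log-scale power is about 63%.

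**Step 7: paired test in the study arm.** Reduction 0.9, assumed correlation 0.5, baseline zeros 5%, 10% and 20%. Of 23 pairs, 18.2, 15.3 and 11.2 remain. Power falls from 89%, 88% and 85% (raw, all pairs) to 69%, 58% and 41% (log, zeros missing). At 10% zeros the fall is from 77% to 42% with correlation 0.3, and from 98% to 81% with correlation 0.7.

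**The case against.** The strongest reply is that the order-of-steps fault is mostly clumsy wording. The intent can be guessed, and even the literal rule costs little for strictly positive outcomes. That is right about size. It does not make the sentence usable, because its stated order and stated purpose both conflict with the guessed intent.

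The Borg harm also depends on what happens to zeros and how many there are. The plan names SPSS 16.0, whose behaviour was not tested. In numpy, exp(log(0)) returns 0, and the literal rule there becomes an untransformed t-test on everyone with nothing lost. Post-walk scores may contain almost no zeros, as Step 6 shows. The main scenarios use low baselines, where a reduction of 0.9 is 40%, 50% and 71% of the control mean (0.9/2.22, 0.9/1.79, 0.9/1.26), and nothing in the documents supports an effect of that size. All of this stands and widens the range at the mild end. It does not remove the fault: resting scores are also taken, 0 is a valid answer, and the result should not depend on how software treats ln(0).

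Finally, the stated study period ends in February 2018 and the document is dated December 23, 2018, so it may be too late to change the plan before unblinding. The dates do not show that unblinding has happened, but timing bears on how a change should be recorded.

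**Conclusion.** The point holds. As written, the plan's only remedy for non-normality returns the original data for positive values, and under either reading it is undefined for a valid score on a listed outcome.

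For strictly positive variables the consequence is small: 1 to 2 points of power at log-SD 0.2 to 0.3, about 5 points at 0.5, and no inflation of type I error. For Borg, harm arises only if the score is judged non-normal and zeros become missing. It then runs from slight, when almost nobody scores 0, to a loss of 23, 30 and 39 points of between-group power at control zeros of 5%, 10% and 20% (SD 1.2, reduction 0.9), with the estimated benefit reduced by about a quarter to a third. The documents give no zero shares or distributions, so the size in this trial is unknown. The wording fault is certain, and it should be corrected.

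**What to change.** Replace the sentence with text such as:

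> Strictly positive, right-skewed variables are analysed by the independent and paired t-tests on the natural-log scale. Only the resulting estimate and its 95% CI are back-transformed, to ratios of geometric means. All other variables stay on the original scale. The Borg score is not log-transformed. All patients, including those scoring 0, are kept, and the score is compared on its original scale by the planned t-tests, with a rank test as a check (Mann-Whitney between groups, Wilcoxon signed-rank within groups). The scale for each variable is fixed before unblinding.

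Listing the scale variable by variable removes discretion over what counts as right-skewed. For Borg the t-test remains the main result and the rank test is supportive. If the data have already been unblinded, the change should be recorded as made afterwards.

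The cost is SAP wording only, with no extra patients or data. Logged variables would be reported as ratios instead of differences in mean ± SD. The Borg t-test treats the scale steps as equal, which is why the rank test is added. In the Step 4 scenarios the rank test on all patients has power within about 2 points of the t-test.

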
Student's 't' test within two specific measurements of different durations of each group ,will be done. In the interpretation of results, ≤ 0.05 level of probability (p) will be accepted as significant.

Expected outcome:

Supplementation of vitamin D₃ may cause statistically significant improvement in lung function test along with exercise tolerance in moderate stable COPD patient.

Keywords:

COPD, VitaminD₃, FVC, FEV1, FEV1/FVC%, FEF25-75%, PEFr, SpO₂, 6 Minute Walk Distance, Modified BORG scale

1.Introduction:

Chronic Obstructive Pulmonary Disease (COPD) is one of the major causes of chronic morbidity and mortality throughout the world (GOLD 2015). Many people suffer from the disease for years and die too early from its complications. COPD is the fourth leading cause of death in adults of United States and also projected to be the third by 2020 (Sabit et al 2007; Eickhoff et al 2008; Finkelstein and Scharf 2009). Though it is a preventable and treatable disease, once developed the disease along with its comorbidities cannot be cured. But its progression and morbidity can be reduced.

In European countries, on the basis of different variables, the prevalence of COPD was ranged from 2.1% to 26.1% (Atsou et al 2011). Additionally it was 8.9% in India (from 6.2% to 13.5%) (Afonso 2011), 17.4% in Copenhagen (aged \geq 35 years) (Fabricious et al 2011) and 3.7% in Abu Dhabi (age 40 to 80 years) (Al Zaabi et al 2011). In Bangladesh among >40 years population it is 21.24%, which suggests an overall prevalence of 4.32% in the total population of all age group (Habib et al 2010). Furthermore 90% of COPD deaths occur in low and middle income countries (Murray and Lopez 1997).

COPD is a multicomponent disease, comprising emphysema in the lung parenchyma, large central airway inflammation and mucociliary dysfunction, bronchiolitis and small airway structural changes (Agusti 2005). Together, these separate factors contribute to the chronic airflow limitation that characterizes the condition (Agusti 2005; Lapperre et al 2004). In addition, there is evidence that systemic inflammation and extra pulmonary effects are also common in COPD, although the association between systemic inflammation and systemic manifestations of COPD is still not entirely clear.

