Investigator has applied for formal Clinical trials through www.Clinicaltrials.gov and was granted permission to go on with the trial (Annexure II) .On the first day of enrollment, the objectives, nature, purpose and potential risk of all the procedures used for the study will be explained in detail to each subject, with a cordial attitude giving emphasis on the benefits he might obtain from this study. He will be encouraged for voluntary participation and will be allowed to withdraw himself from the study even after participation, whenever he felt uneasy. If he agreed to be enrolled in the study, an informed written consent will be taken in a prescribed form (Annexure - IV). Detailed family history, medical history and thorough physical examination of each patient will be done and all the information will be recorded in a standard data sheet (Annexure - V). Then all the patients will be requested to attend the Department of Physiology at 9 am (about 1 and 1/2 hours after his breakfast) on the day of biochemical and spirometric examination.

On the examination day, 5 ml of venous blood will be collected and taken to the Hematology laboratory as soon as possible for the estimation of serum 25-hydroxycholecalceferol, serum glucose 2 hours after breakfast and serum creatinine. After that his height and weight will be measured and the spirometric lung function test will be done by using a portable spirometer. After getting all the biochemical and spirometric reports the final selection will be done, according to the inclusion and exclusion criteria.

Subsequently, all the eligible patients will be randomly assigned to either 'Control' or 'Study' groups and will be thoroughly informed about the objectives and detailed study procedure, once again. Then the patients will be examined for the baseline value of all the study variables in Day 1.

Again after 90 days the study variables will be collected from same 46 patients.

CONFOUNDING VARIABLES:

- Age: >40 years (Heideri 2015)
- Socioeconomic condition: Middle class (Martineau et al 2015)
- Smoking status: (Janssens et al 2010)
 - Current smoker = with history of active smoking
 - Ex-smoker = with history of 0 – 8 quit year
 - Duration = for >30 pack years
- BMI: 25 – 29.9 kg/meter-sq (Janssens et al 2010)
COPD patients at moderate stage according to GOLD criteria with > 4 years duration (Rees et al 2013)
- Stable COPD patients (Mehrparver et al 2010)
- Vitamin D₃ deficient: 30 ng/ml (Vitamin D council 2017)

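### The plan does not name the between-group comparison as the test of efficacy or fix its form, and it leaves the day-0 outcome value out of the analysis

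*Combined protocol and SAP*

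**What the plan says.** The Statistical Analysis section plans comparisons of all four classes of variable: "exercise tolerance variables and hematological variables will be found between two groups of patients" ends the sentence that lists them. The tools are an independent-sample t test between groups and a paired t test "within two specific measurements of different durations of each group will be done", with one threshold of p ≤ 0.05 for everything. The Project Summary repeats the pair, describing the second as a "test within two specific measurements of different durations of each group". Variables that are not normal are to be log-transformed first. No adjusted model appears.

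Other sections bear on the form of the comparison:

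- The only comparison among the Specific Objectives is "To compare the results of baseline and endline". The hypotheses speak of improvement and name no comparator.
- The Project Summary says that "exercise tolerance will be assessed by change in 6 Minute Walk Distance (6MWD", which points to change for that variable but ties it to no test.
- For SpO₂ and dyspnoea, the same summary says they "will also be measured both before and after 6MWT to evaluate their change in both the groups". That change is across the walk, and the data sheet has before and after columns for both at day 0 and at day 90.
- No form is given for any spirometric variable.
- Day-0 values are collected for everything: "Then the patients will be examined for the baseline value of all the study variables in Day 1". Standard treatment is prescribed to both groups after that.

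**The concern.** Randomisation protects only the comparison between groups. A before/after gain in group B mixes any D3 effect with whatever else moves both groups over 90 days, including the standard treatment prescribed to all. If the paired test in B is significant and the between-group test is not, the plan has no rule for which result stands, and its comparison objective could be met by the paired test alone.

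The unstated form of the between-group test raises two further matters. If the form is settled only once the data are seen, the false-positive rate for that outcome rises. And both unadjusted forms give up power that the recorded day-0 value could supply, in a trial of 46 patients.

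**Working it through.** **Inputs.** From the protocol: 23 patients per group, threshold 0.05, measurements at day 0 and day 90. Assumed, because the documents give no value: two-sided tests, normal data, a gain d common to both groups (in SD of the change), the day-0/day-90 correlation r, and a true difference of 0.5 SD of the outcome. The protocol gives no effect size, SD or power, so there is no stated figure to reproduce.

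**1. Paired tests when D3 does nothing.** The paired statistic is noncentral t with 22 df and ncp = d × √23 = 4.796d; the critical value is 2.074. Let U and L be the chances of a significant gain and a significant loss in one group. Improvement significant in B but not in A has probability U × (1 − U − L). The last column adds the condition that the between-group t test on change is not significant. It comes from simulation (400,000 trials per d).

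| d | U | L | U(1 − U − L) | and between-group test not significant |
|---|---|---|---|---|
| 0 | 2.5% | 2.5% | 2.4% | about 2% |
| 0.1 | 6.7% | 0.8% | 6.2% | about 5% |
| 0.2 | 14.9% | 0.2% | 12.6% | about 11% |
| 0.3 | 28.0% | 0.04% | 20.1% | about 18% |

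The last two columns are shares of all trials. The between-group test itself stays at 5% whatever d is. One SD of the change is √(2(1 − r)) SD of the outcome, so d = 0.3 is 0.30 SD of the outcome at r = 0.5 and 0.19 SD at r = 0.8.

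**2. Form chosen after seeing the data.** In 400,000 null trials per r, count a trial as positive if either the day-90 t test or the change t test is significant (44 df, critical value 2.015).

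| r | 0.3 | 0.5 | 0.7 | 0.8 | 0.9 |
|---|---|---|---|---|---|
| Either form, two-sided | 8.8% | 9.1% | 9.4% | 9.5% | 9.6% |
| Either form, false benefit | 4.4% | 4.5% | 4.7% | 4.7% | 4.8% |

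The nominal figures are 5% and 2.5%. ANCOVA alone stays at about 5% two-sided.

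**3. Power for a 0.5 SD difference.** For the t tests, ncp = (0.5/k) × √(23/2) = 1.696/k, with k = 1 for day-90 values and k = √(2(1 − r)) for change. At r = 0.3, for example, k = √1.4 = 1.183 and ncp = 1.433. ANCOVA was simulated with 43 df and its exact standard error, which allows for chance baseline imbalance.

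| r | 0.3 | 0.5 | 0.7 | 0.8 | 0.9 |
|---|---|---|---|---|---|
| Day-90 values | 38% | 38% | 38% | 38% | 38% |
| Change | 29% | 38% | 57% | 75% | 96% |
| ANCOVA | 41% | 47% | 63% | 78% | 96% |

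ANCOVA gains about 12, 9, 6, 3 and 0 points over change, and about 2, 9, 25, 40 and 58 points over day-90 values.

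**The case against.** The strongest reply is that the plan already contains a valid randomised comparison of all four classes of variable, and that nothing in it says a paired result will be read as efficacy. That stands: a reader might infer that the plan judges D3 by the paired tests, but the text shows only that the priority is unstated.

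The size of the paired-test problem also rests on an assumed shared gain. Patients must have had no change in routine medication for 4 weeks and more than 4 years of disease, and the documents do not say whether the standard treatment is new to them. With no shared gain, the split between B and A is no commoner than 2.4%. A reader could make the conflict look larger by quoting it as a share of the split trials only (about 66% to 88%). Those are percentages of an uncommon event, so the shares of all trials are the fair measure.

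Nor do the documents support saying that the error rate is doubled as planned. The figure of about 9% needs an analyst who tries both forms and reports the better one, and for 6MWD the word change already narrows the choice.

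A t test on change is valid, and naming either form in advance would cure the error-rate problem. ANCOVA is preferred because it does at least as well at every r examined, so r need not be guessed; at high r its advantage over change is small.

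It is tempting to say that the SpO₂ and dyspnoea outcomes are undefined. Study Variables lists resting SpO₂. The Introduction, the Specific Objectives and the placing of dyspnoea under exercise tolerance point to the post-walk score. Only confirmation is needed. The matching and similarity stated for the confounders restrict those variables; they are not an adjustment for the day-0 outcome value, and no separate criticism of them is made here.

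**Conclusion.** The gap is real and should be fixed. The plan does not make the between-group test decisive, does not fix its form (apart from a pointer to change for 6MWD), and does not use the day-0 value. It is a gap in specification, not a stated rule that gives a wrong answer.

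The chance that the plan yields conflicting results with no rule to settle them ranges from about 2% to about 18% over the gains examined, and is more plausibly near the low end. The choice of form matters only if it is left until the data are seen. The power gain from ANCOVA is large against day-90 values when r is high, moderate against change when r is low, and negligible against change at r = 0.9. These sizes depend on the assumed d, r and 0.5 SD difference; the gap in the text does not. Parts of the document were not available for this review, but the Statistical Analysis section reads as complete.

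**What to change.** - State that the conclusion on D3 for each outcome rests only on the between-group contrast.
- Replace the unadjusted t test with ANCOVA: day-90 value on group, with that outcome's day-0 value as covariate. Report the adjusted difference with its 95% CI. Where the log transformation is used, put both values on the log scale.
- Keep the paired tests, labelled descriptive and not as evidence of a D3 effect.
- Reword the last specific objective to compare the groups at day 90 given baseline.
- Say whether post-walk SpO₂ is tested as well as resting SpO₂, and confirm the time point of the dyspnoea score.

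The cost is one degree of freedom per model and some wording; the day-0 values are already collected. Timing needs care: the stated study period ends in February 2018 and the document is dated December 23, 2018. If data collection has already ended, fix the choice before unblinding. If that is no longer possible, report it as a later decision.
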